In this proposed study, each participant will undergo 2 study phases, and each response variable will be measured *at least* once per phase. Thus, for each response measure we will have at least 50×2 paired observations. Based on preliminary data analysis, we have estimated an effect size (mean paired difference) of 0.69 ± 0.36 g for fat mass and an effect size (mean paired difference) of 0.91 ± 0.65 g for weight gain. This translates to very large effect sizes of 1.92 (fat mass) and 1.4 (weight gain) for paired t-tests. With these effect sizes we will have >80% power for paired t-tests with our expected sample size and will have sufficient power to test for differences between pre- and post-menopausal women.

Eighty pre- and postmenopausal women, age 20-65 y i with an overweight BMI (25-29.9 kg/m²) ii will be recruited from the New York City area. These women will come from the pool of participants in the Population Science project in this Center application. Pre-menopausal women will not be on oral contraceptive medications and post-menopausal will not be on hormone replacement therapy. In addition, women recruited to participate in this study will habitually sleep 7-9 h/night, will be free of any current and past sleep and psychiatric disorders, including eating disorders (ex. anorexia, bulimia, night eating syndrome), and will not have type 2 diabetes or CVD (**Table 2**) iii. We will exclude women taking medication to reduce blood pressure and cholesterol levels. Smokers (defined as currently smoking any cigarettes or ex-smokers <3 y), non-day and rotating shift workers, persons who plan to travel across time zones within 4 weeks of the study, and those with a history of drug and alcohol abuse, drowsy driving, or excessive caffeine (>300 mg/d) or alcohol intakes >2 drinks/day) will also be excluded. Further, we will not enroll women who have had a recent weight change or who actively participated in a diet or weight loss program in the previous 3 mo, and those with a neurologic condition that may disrupt the procedures. Women who are pregnant or <1 y post-partum, and those with contraindications for MRI scanning will be excluded iv. All participants will have normal scores on the

ⁱ See Amendment 1b

ii See Amendment 1c

iii See Amendment 1d

iv See Amendment 1a

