This study will be a randomized, crossover, outpatient SR study with 2 phases of 6 weeks each. Sleep duration in each phase will be the participant's regular bed- and wake-times during the HS phase and HS minus 1.5 h in the SR phase. During the HS phase, participants will be asked to follow a fixed bedtime routine based on their screening sleep schedule. During the SR phase, participants will be asked to keep their habitual wake time constant but delay their bedtime to achieve a reduction of 1.5 h in total sleep time. A delay in bedtimes was chosen rather than advancing wakeup time because it likely most closely reflects differences in sleep timing behavior between short and normal sleepers. Spaeth and colleagues have also shown that restricting sleep to the latter portion of the night is associated with increased food intake and weight gain relative to HS (8). We also considered providing fixed bed- and wakeup times for all women but decided to provide individualized bedtimes and wakeup times to reduce variability in our sample.

On the first day of each study phase (baseline), participants will come to the Clinical Research Resource (CRR) of the Irving Center for Clinical and Translational Research (CTSA) at CUMC in the morning after an overnight, 12 h fast. Participants will have anthropometric measurements taken and will then be taken to the department of Radiology to undergo magnetic resonance imaging (MRI) scanning to assess body composition. They will then return to the CRR for an oral glucose tolerance test. Participants will begin the fixed bedtime routine that night. These baseline measurements will be

repeated at endpoint, 6 weeks later. Body weight and waist circumference will be measured weekly and fasting blood samples will be taken bi-weekly during adherence check visits v.

Recruitment and blinding

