Women who fit the general inclusion/exclusion criteria for this study will be identified from the Population Science project and invited to participate in this project. Women who express an interest in participating will undergo a preliminary phone screening. During this phone interview, more details of the study will be provided to the prospective participant and additional information will be obtained to determine potential eligibility. Women who pass the phone screening and are interested in participating in the study will be scheduled for an in-person screening. At this second screening point, eligibility will be ascertained. From there, sleeping behavior will be established. This will be done with actigraphy over a 2-week period.

Two weeks prior to randomization and during the washout period, participants will wear an actigraph (Micro Motion Logger Sleep Watch, Ambulatory Monitoring, Inc., Ardsley, NY) vi and keep a sleep diary to verify sleep duration and sleep-wake schedule. In addition to achieving an average sleep of 7-9 h/night, by wrist actigraphy. participants will only be enrolled if they achieve 7 h of sleep for at least 10 of the 14 nights of screening and have <4 nights with <6 h of sleep vii. At the time of randomization, a urine pregnancy test and drug screen will be performed. Participants will be asked to abstain from caffeine and alcohol intake for 24 h prior to the start of each study phase. Between study phases, if participants have not returned to baseline sleep patterns, an additional 2-4 week washout period will be provided. In general, washout periods will be 6 weeks in duration. This washout length will ensure that women are in the same phase of their menstrual cycle at the start of each experimental phase (Fig. 3).

[figure not shown]

Figure 3. Study protocol. Participants will undergo a 2-wk screening to assess eligibility prior to randomization to their first study phase: restricted or habitual sleep. At baseline, body composition will be assessed and blood samples will be taken. Compliance with the sleep protocol will be assessed weekly, along with weight measurements. A blood sample will be taken bi-weekly. Baseline measurements will be repeated at endpoint (6 wk). Participants will undergo a 6-wk washout period before undergoing phase 2.

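### The 6-week washout does not guarantee that premenopausal women start both phases at the same cycle point, and the analysis does not allow for misaligned starts

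*Combined protocol and SAP*

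**What the plan says.** The Overview of study design describes a "randomized, crossover, outpatient SR study with 2 phases of 6 weeks each", comparing sleep restriction (SR) with habitual sleep (HS). Baseline measurements in each phase are "repeated at endpoint, 6 weeks later".

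Recruitment and blinding makes three statements about the washout, in this order:

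- An exception triggered by sleep alone: "if participants have not returned to baseline sleep patterns", then "an additional 2-4 week washout period will be provided".
- The usual length: "In general, washout periods will be 6 weeks in duration".
- The property claimed for it: "This washout length will ensure that women are in the same phase of their menstrual cycle at the start of each experimental phase".

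The Figure 3 legend gives only the usual length: "Participants will undergo a 6-wk washout period before undergoing phase 2".

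Under Study population, "Pre-menopausal women will not be on oral contraceptive medications", so natural cycles are to be expected. The covariates listed under Linear Mixed Model Analyses are age, baseline BMI and race/ethnicity. The preliminary phase term in the Statistical analysis plan concerns the study phase, not the menstrual one. No section describes recording menses or timing a phase start to the cycle, and the amendments change neither the washout nor this.

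**The concern.** The claim of alignment is stated without conditions, but it depends on two that the plan does not secure: a cycle length that divides the start-to-start interval, and no extension that shifts the second start.

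The planned regressions and paired tests use the baseline-to-week-6 change. If an outcome varies with the cycle, that change contains a cycle component, because baseline and endpoint fall at different cycle points. With aligned starts the component is the same in both phases and drops out of SR minus HS. With misaligned starts some or all of it remains. At stake is precision in premenopausal women, chiefly for outcomes measured only at baseline and endpoint, such as the glucose tolerance test.

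**Working it through.** **Inputs from the documents.** Phase length 42 days; usual washout 42 days; extension 14 to 28 days; baseline to endpoint 42 days.

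**Assumptions.** Cycle length L is not given: 28 days is taken, with 25, 26 and 30 as alternatives. The cycle effect is modelled as a cosine of amplitude A, which is also not given.

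**1. The plan's own claim.** Start-to-start interval T = 42 + 42 = 84 days. 84 / 28 = 3.00 cycles. The claim reproduces for a 28-day cycle and a 6-week washout.

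**2. With the permitted extension (L = 28).**

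| Extension | T (days) | T / 28 | Days out |
|---|---|---|---|
| none | 84 | 3.00 | 0 |
| 2 weeks | 98 | 3.50 | 14 |
| 3 weeks | 105 | 3.75 | 7 |
| 4 weeks | 112 | 4.00 | 0 |

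**3. Other cycle lengths, no extension (T = 84).**

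- L = 25: 84 − 75 = 9 days out.
- L = 26: 84 − 78 = 6 days out.
- L = 30: 90 − 84 = 6 days out.

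**4. What remains in SR minus HS.** 42 / 28 = 1.5 cycles, so endpoint lies half a cycle from baseline and a single change can carry up to 2A. For the difference between the two phases' changes, the largest remaining cycle component is

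4A × |sin(42π/L)| × |sin(πT/L)|.

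For L = 28 the first sine is 1 in size, which gives:

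- no extension: 4A × 0 = 0
- 2 weeks: 4A × 1 = 4A (the two shifts have opposite sign and add)
- 3 weeks: 4A × 0.707 = 2.83A
- 4 weeks: 4A × 0 = 0

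For the other cycle lengths without extension:

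- L = 25: 4A × 0.844 × 0.905 = 3.06A
- L = 26: 4A × 0.935 × 0.663 = 2.48A
- L = 30: 4A × 0.951 × 0.588 = 2.24A

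**5. Noise or bias.** If women enter at random cycle points, the component averages to zero and its SD is the peak divided by √2. At L = 28 this is 2.83A after a 2-week extension and 2.0A after 3 weeks. A simulation of one million women with random start point and random sequence gave SDs of 2.828A and 2.001A, with means within 0.01A of zero.

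A non-zero mean needs two things together: a common start point in the cycle, and extension rates that differ by sequence. As an illustration with assumed rates, suppose all women start at the cycle peak, sequences are equal in size, and 30% of SR-first and 10% of HS-first women are extended by 2 weeks. The bias is then 0.5 × 0.30 × 4A − 0.5 × 0.10 × 4A = 0.4A in size. With equal rates it is 0.

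**The case against.** **The two statements do not collide.** A reader might infer a flat contradiction between extension and assurance. The documents do not support that: the assurance follows the sentence on the usual 6 weeks and attaches to that length, and the extension is a separate exception. This stands. The fault is that the assurance is not carried over to the exception, and that it is too strong even for the usual length once cycles differ from 28 days.

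**Not every extension misaligns.** This also stands: 4 weeks restores alignment on a 28-day cycle.

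**The extension has its own purpose.** It lets sleep recover before the second phase, which limits carryover. Accepting some cycle noise in exchange is defensible. Alignment is mentioned once, and no aim, model or power statement rests on it. The remedy below therefore works through recording and analysis and leaves that safeguard alone.

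**The loss may be small.** Weekly blood pressure, weight and waist readings enter mixed models using all time points, and readings spread over 1.5 cycles average out part of a cycle effect. Glucose tolerance and MRI measurements remain two-point, although nothing in the documents indicates a cycle effect on visceral fat. Postmenopausal women are unaffected and dilute the noise in the pooled analysis.

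**A percentage is tempting but unsupported.** Suppose the half-cycle shift has root-mean-square size c = 0.25 to 0.5 SD of the paired difference, and 10 to 30% of premenopausal women are extended by exactly 2 weeks. Their contrast variance then rises by 0.10 × (2 × 0.25)² = 2.5% to 0.30 × (2 × 0.5)² = 30%. If c is instead the peak shift and start points are random, the range halves to 1.25 to 15%. Every input is assumed, so none of this is a finding. Even a 30% rise would leave the stated effect sizes at 1.92/√1.3 = 1.68 (fat mass) and 1.4/√1.3 = 1.23 (weight), still very large for 50 completers.

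**Conclusion.** The point holds as a minor one. The protocol claims a property that its schedule does not guarantee. On a 28-day cycle it holds with no extension and with 4 weeks, and fails by 14 days at 2 weeks and 7 days at 3 weeks. For cycles of 25, 26 or 30 days it fails by 6 to 9 days even with no extension. The plan neither records nor adjusts for this.

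The consequence is added within-woman noise in the SR minus HS change for affected premenopausal women, up to 4A at worst on a 28-day cycle. The figures rest on the assumed cycle lengths and a regular cosine-shaped effect. An absolute size cannot be given, because neither A nor the number of extended washouts is in the documents.

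A reader might go further and infer bias, since the extension depends on sleep recovery and could fall more often on women who had SR first. The documents do not support this. They give no extension rates by sequence and no common cycle point for the first start, and both would be needed.

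**What to change.** - **Text.** Reconcile the extension with the same-phase statement, and replace the guarantee with a description of what the schedule delivers. The washout rule itself is for the investigators.
- **Data.** Record the date of last menses at the baseline and endpoint visits of each phase (four dates per premenopausal woman) and the actual washout length.
- **Model.** Adjust for cycle phase in premenopausal women, for example with a time-varying term set to zero for postmenopausal women so that the pooled model stays intact.
- **Sensitivity analysis.** Repeat the SR minus HS comparisons without premenopausal women whose two starts were not cycle-aligned.
- **If data collection is over.** The amendment notes refer to accrued participants, so new fields may no longer be possible. Visit dates still give each woman's start-to-start interval, so those with an extended washout can be identified and excluded in the sensitivity analysis.

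Cycle dates would also help the exploratory pre- versus postmenopausal comparison. It uses the SR-phase change alone, so no HS phase is subtracted to remove a cycle shift.

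The cost is a sentence of protocol text, one date field per visit, and one or two degrees of freedom. Self-reported cycle dates carry some error.

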Participants will be blinded to the purpose of the study to ensure that they do not alter their habits from knowledge that SR may cause alterations in food intake and physical activity, resulting in weight gain. Participants will be told that the purpose of the study is to assess the effects of mild SR on mood and cognitive and physical performance. Questionnaires and performance tests will be administered at baseline and bi-weekly to maintain blinding.

Details of the study procedures

Ensuring adherence to the sleep protocol.

We have a well-defined strategy for ensuring adherence to the sleep protocol in this outpatient setting. Participants will be given written instructions on study procedures and investigator phone calls will be made as reminders of the bedtimes and wakeup times on a weekly basis viii. To verify that participants adhere to the sleep protocol, they will be asked to keep a sleep diary and wear an activity monitor 24 h/day. Participants will wear a Motionlogger actiwatch on their wrist (Ambulatory Monitoring, Inc, Ardsley, NY) ix, which will serve to track their sleep duration, sleep timing, and ambient light. This watch is water resistant and therefore does not need to be removed to shower or swim. To further ensure compliance with the sleep protocol, participants will be required to come to the research center on a

^v See Amendment 2c

vi See Amendment 2a

vii See Amendment 1e

viii See Amendment 2b

ix See Amendment 2a

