weekly basis. This weekly visit will serve several purposes: (1) to download data from the actiwatch (verify sleep duration); (2) to charge the watch; (3) to obtain weekly diaries (verify bedtimes and wakeup times) and other questionnaires; (4) to obtain body weight, waist circumference, and blood pressure measurements and blood samples (bi-weekly only). Participants will be told a priori, as part of the screening process, that they must adhere to the sleep protocol for continued participation in the study and that adherence will be checked weekly. Non-adherent participants will be terminated from the study. Adherence will be defined as having bedtimes and wake times within 30 min of scheduled times at least 5 days/week and achieving an average of >7 h of sleep each week with no more than one night of sleep <7 h during the HS phase and achieving an average sleep reduction of 1.5 h from screening sleep duration each week with no more than 1 night with <1.5 h of restriction during the SR phase. Daytime naps will not be permitted. Participants will receive weekly incentives, in the form of a gift card, for their continued adherence to the sleep protocol.

Blood sampling procedures.

Fasting blood samples will be taken at baseline, 3 weeks, and endpoint of each sleep phase for the measurement of metabolic risk factors: glucose, insulin, and inflammatory markers *. An oral glucose tolerance test will be performed at baseline and endpoint as well. Two baseline blood samples (8 mL) will be obtained at 10 and 5 min before glucose ingestion (-10 and -5). At time 0, participants will consume 75 g of glucose in 300 mL solution orally. Subsequent blood samples (10 mL) will be obtained at 15-, 30-, 60-, 90- and 120-min post-intake. These procedures will be performed by a certified nurse in the CRR at CUMC.

Details of the outcome measures

Blood pressure measurements.

Blood pressure will be measured weekly with the participant sitting, with their legs uncrossed, for at least 5 min. Measurements will be taken twice from the non-dominant arm using an appropriately sized cuff. In addition, participants will wear a blood pressure monitor for 24 h at baseline, 3 weeks, and 6 weeks of each intervention xi.

Body composition measures.

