Anthropometric measurements will be obtained at the New York Obesity Research Center Human Phenotyping/Body Composition Core Laboratory. A single trained technician will obtain all measurements for this study using standard procedures in the laboratory. Height, weight, and body circumferences (waist and hip) will be measured in duplicate with the participant wearing only a hospital gown and no shoes.

Whole-body MRI will be carried out with a T1-weighted, fast spin-echo sequence, with a 210 ms TR and a 17 ms TE using a 1.5T General Electric system (6X Horizon, Milwaukee, WI). A field of view of 48 cm and a 256 x 256 matrix will be used. Participants will be positioned in a supine position with their arms stretched overhead in the scanner. The scanner will be landmarked at the L4-L5 intervertebral disc and images from L4-L5 to the top of the fingerprints and from L4-L5 to the end of the toes. Images will have a slice thickness of 1 cm and will be spaced 4 cm apart for the upper and lower body but 2 cm apart for the visceral area, demarcated as 10 cm below to 20 cm above L4-L5. Shen and colleagues have reported that estimate errors in assessing total visceral adipose tissue and subcutaneous adipose tissue increased with increasing distance between images (9). The percent difference between estimated and actual volumes for visceral adipose tissue was 3.14% with the 2-cm inter-slice interval vs 9.70% with the 5-cm inter-slice interval, corresponding values for subcutaneous adipose tissue were 0.26 and 0.85%. Since a primary outcome of interest is visceral adipose tissue, we chose to perform the image acquisition with a 2-cm inter-slice interval rather than the typical 5 cm. *Cardio-metabolic risk assessment*.

All samples will be analyzed in the Hormone and Metabolite Core laboratory of the NYORC by skilled technicians ^{xii}. Insulin will be assayed using a radioimmunoassay (RIA; Linco Research Products Inc., St. Charles, MO; mean inter-assay CV of 4.5% (10, 11). Tumor necrosis factor-α will be assessed with

x See Amendment 2d

xi See Amendment 2d

xii See Amendment 2f

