Exploratory Hypothesis: The effects of prolonged SR on adiposity and cardio-metabolic risk factors will be greater in pre-menopausal women relative to post-menopausal women. We will first compute the effect of SR on adiposity and cardio-metabolic risk factors. This will be computed as the increase in SR from the baseline value of the SR-phase on each measure of adiposity and cardio-metabolic risk factors for each woman. Then these differences will be compared between pre- and post-menopausal women by means of a linear model analysis, one-sided unpaired t-test and Wilcoxon test. The comparison by linear models will be done by using the (SR vs. baseline) difference as the outcome (separately for each of adiposity and cardio-metabolic risk factors) and menopausal-status (pre- vs. post) and the covariates as independent variables. Paired one-sided t-test and Wilcoxon test will be used to determine whether the menopausal-status (greater in pre- vs. post-, to be used as the two groups for the tests) is associated with greater average difference (SR vs. baseline) in adiposity and cardio-metabolic risk factors.

ETHICAL ASPECTS OF THE PROPOSED RESEARCH Protection of human subjects

All personnel involved in this project, including fellows who will be trained as part of the Center grant, will undergo human subjects research training. Courses include ethical considerations of human subjects research and health information privacy rules. Research will not be performed until approval from our Institutional Review Board is obtained. All participants will be informed of the study procedures during the screening and consenting process and will be given the opportunity to ask questions about the study. Furthermore, participants will be informed that they can withdraw from the study at any time without jeopardizing their future care at our medical center.

All data will be kept on file coded (de-identified) with a study number and without any specific identifying personal health information. Study data will be stored on password-protected, encrypted end-point devices. All paper files will be stored in locked cabinets. Imaging data will be stored (de-identified) in a secure computer database that is protected by firewalls and passwords. MRI data will be transferred to the New York Image Reading Center via secure servers. Only personnel immediately involved in the study will have access to study files and documents.

Potential risks & risk management

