AMMENDMENTS TO THE PROTOCOL (Listed in chronological order within sections)

- 1. Eligibility criteria modifications:
 - a. History of fainting was added as an exclusion criteria.
 - b. The upper age limit was removed from eligibility criteria to enhance recruitment of postmenopausal women.
 - c. Inclusion criteria for weight status was extended in both directions to include women with BMI 30-33 kg/m² as well as 20-24.9 kg/m²; women with BMI 20-24.9 kg/m² were required to have elevated familial risk for CVD (family history [1 or more parent with] of type 2 diabetes, cardiovascular disease, or hypertension) to be considered for participation.
 - d. Women with stable (>3 mo) controlled hypertension (but not resistant hypertension) or diabetes (HbA1c <7%) or stable use of cholesterol-lowering medication were considered for study participation in order to enhance enrollment of postmenopausal women.
 - [Note: No accrued participants reported any of the above. All met initial eligibility criteria related to cardio-metabolic health.]
 - e. Women who slept 7 or more hours per night for at least 70% of screening time (at least 14 days) were eligible for this study. Previous requirement stated 10/14 nights with 7 or more hours of sleep/night **and** average sleep of 7 or more hours during the 14 days. This amendment removed the requirement for average sleep duration of 7 hours/night or more. This was to enhance enrollment of postmenopausal women who naturally have shorter sleep duration than premenopausal women.

[Note: All accrued participants met the original, more stringent sleep-based criteria.]

- 2. Study procedure modifications:
 - a. The tri-axial accelerometry device as well as its placement (on body) and duration of use were modified. The Actigraph GT3X+ (Actigraph, Pensacola, FL) replaced the Motionlogger. This device was worn on the non-dominant wrist continuously during screening and for the full duration of each study phase to ensure compliance with the sleep duration requirements. In addition, hip-worn actigraphy (originally planned to be assessed via Actigraph GT3X+) was eliminated, since physical activity and inactivity can be derived from the wrist-worn device.
 - b. Rather than providing weekly phone-call reminders of sleep assignments, study staff provided participants with written target nightly target bed and waketime schedules each week. Email reminders were sent throughout each study phase to complement weekly in-person meetings.

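### No one who takes seated blood pressure or reads visceral fat is masked to phase, although the study team must know it and both outcomes are tested one-sidedly for an increase under SR

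*Combined protocol and SAP*

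**What the plan says.** **Masking.** The only provision is in Recruitment and blinding: "Participants will be blinded to the purpose of the study to ensure that they do not alter their habits". It concerns the purpose of the study and applies to participants. No section says that the staff who take blood pressure, the anthropometry technician or the MRI reader are kept unaware of the phase.

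**Who must know the phase.** Under Ensuring adherence to the sleep protocol, the rule differs by phase. In the SR phase it requires "achieving an average sleep reduction of 1.5 h from screening sleep duration each week"; in the habitual sleep (HS) phase it requires an average above 7 h. Under Amendment 2b, "study staff provided participants with written target nightly target bed and waketime schedules each week".

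**What happens at the weekly visit.** The same section combines the adherence check with outcome measurement: "This weekly visit will serve several purposes: (1) to download data from the actiwatch (verify sleep duration") is one listed purpose, and another is "("4) to obtain body weight, waist circumference, and blood pressure measurements and blood samples (bi-weekly only")".

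**Who measures.** For anthropometry (Body composition measures): "A single trained technician will obtain all measurements for this study using standard procedures in the laboratory". For imaging (Protection of human subjects): "MRI data will be transferred to the New York Image Reading Center via secure servers". Blood pressure measurements specifies two seated readings on one arm, but neither the device nor the person taking them.

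**How the outcomes are tested.** The Statistical analysis plan uses one-sided paired t and Wilcoxon tests for an increase under SR, for blood pressure (Aim 1) and for MRI adiposity variables (Aim 2). Body composition measures counts visceral adipose tissue as a primary outcome. Amendment 2e reduces 24-hour ambulatory blood pressure to a single endpoint measure.

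**The concern.** Participants cannot be masked to how long they sleep, so protection against expectation has to come from the people who measure. The plan gives them none. The team knows the phase and the direction of the hypothesis, and it sees each woman for adherence and for blood pressure at the same visit.

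A tendency to read slightly higher at the end of SR than at the end of HS would follow the treatment. The crossover removes stable differences between women but not an error that moves with the phase. A single trained technician and duplicate readings limit variation between and within observers, but they do not remove expectation.

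The less observer-dependent ambulatory measure has no within-phase baseline after Amendment 2e. It therefore cannot supply the change from baseline to week 6, and the seated readings have to. At stake is the error rate of the Aim 1 blood pressure test and of the Aim 2 visceral fat test.

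**Working it through.** **1. The plan's own figure.** The sample size section has no calculation for blood pressure or visceral fat. It gives effect sizes for fat mass, 0.69/0.36 = 1.92, and for weight gain, 0.91/0.65 = 1.40, and states power above 80%. With 50 pairs (noncentral t, 49 df, alpha 5% assumed because none is stated), power exceeds 99.9% for both. The stated figure therefore reproduces, and masking would not alter it. With 50 pairs, the smallest effect detectable with 80% power is 0.36 SD one-sided or 0.40 SD two-sided.

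**2. Which bias matters.** Let *e* be the average observer error. If the paired test is run on changes from baseline, the bias in the SR-minus-HS difference is

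b = (e at SR week 6 − e at SR baseline) − (e at HS week 6 − e at HS baseline).

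Error that is equal at baseline and week 6 of a phase cancels. Error that differs does not. A difference is plausible: the sleep routine starts on the night of the baseline visit (Overview of study design), so no SR effect is expected at baseline, while one is expected at week 6.

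**3. Inputs for blood pressure.** n = 50 completers (documents). One-sided alpha 5% (assumed). SD of the paired difference 8 mm Hg, range 6-10 (assumed; none is given). b = 1 or 2 mm Hg (assumed; the documents give no basis for any value). True effect zero.

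**4. Formula.** Normal approximation: rejection rate = 1 − Φ(1.645 − b/(SD/√50)). For SD 8 and b = 1: SD/√50 = 1.131, 1/1.131 = 0.884, and 1 − Φ(0.761) = 0.223. The noncentral t gives 0.220. Noncentral t results:

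| SD (mm Hg) | b (mm Hg) | b/SD | One-sided 5% | Two-sided 5% |
|---|---|---|---|---|
| 6 | 1 | 0.167 | 31.5% | 21.1% |
| 8 | 1 | 0.125 | 22.0% | 13.9% |
| 10 | 1 | 0.100 | 17.2% | 10.7% |
| 6 | 2 | 0.333 | 75.2% | 63.7% |
| 8 | 2 | 0.250 | 53.9% | 41.0% |
| 10 | 2 | 0.200 | 40.1% | 28.4% |

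**5. Visceral fat.** No SD is given, so the result can only be stated in SD units of the paired difference. A bias of 0.10, 0.20 or 0.30 SD gives 17%, 40% or 67% one-sided, and 11%, 28% or 55% two-sided.

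**The case against.** The strongest reply is that the documents show a silence and not a fault. Several stronger readings are tempting, and the text does not support them.

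- **That staff check sleep first and then measure.** The weekly visit section numbers the purposes of the visit; it does not set a sequence. Reordering the visit would also mask nobody who already issues the schedules.
- **That the same person does both tasks.** This is not stated. The anthropometry technician works in a core laboratory and may be separate, and blood pressure is not assigned to anyone.
- **That waist is tested one-sidedly.** No test names waist; Aim 2 names MRI variables.
- **That coding by study number leaves the phase visible to the MRI reader.** Scan labels are not described. In a randomised crossover, visit or date alone does not reveal SR or HS without the sequence, and nothing says the reading centre holds it. The segmentation method is not described either.
- **That one-sided testing causes the problem.** It does not. The two-sided rates above are also inflated; a one-sided test gives the whole alpha to the expected direction.

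It is also fair that an automated cuff would remove much of the mechanism for blood pressure, that glucose tolerance in Aim 1 rests on blood samples, and that the size of the bias is assumed. All of this stands. It limits the point to an open route for bias. It does not supply the missing masking: a privacy code is not a commitment to masked reading, and an unstated device is not a commitment to an automated one.

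**Conclusion.** The point holds as a gap in design protection. No assessor masking is planned for seated blood pressure or visceral fat, the study team necessarily knows the phase, and both outcomes are tested in the expected direction only. The documents do not show that bias occurred or that any particular assessor knew the phase.

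The size is a sensitivity statement only. With 50 pairs, alpha 5% and an SD of 6-10 mm Hg, a 1 mm Hg differential bias raises the one-sided false-positive rate from 5% to about 17-32% (two-sided, about 11-21%). At 2 mm Hg it is about 40-75% (two-sided, about 28-64%). Every input except the 50 is assumed. The result depends on bias that differs between baseline and week 6 according to phase, and on a blood pressure method open to observer influence. This is more than a missing detail because masked MRI reading would protect a primary outcome at very little cost.

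**What to change.** **MRI.** Send the files to the existing reading centre under random scan codes with phase, visit and date removed. Read all scans of one woman together in random order, and link codes to phase only after the readings are locked. Stored scans can be recoded and read in this way. If they have already been read, report what the reader could see.

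**Blood pressure.** The amendments are written in the past tense, so visits may be over. Where any remain, have existing staff who neither check adherence nor issue schedules take the readings, keep the phase off the recording sheet, and name the device. Otherwise report who measured, with what device, and whether they knew the phase.

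**Cost.** Mainly relabelling: two scans in each of two phases is four per completer, or about 4 × 50 = 200 scans. Sample size and endpoints do not change. Masking of blood pressure stays partial, because a woman may disclose her phase.
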